12.1.9 Analysis of the DIAN-TU-001 Cognitive Composite Score and its Components

These analyses will be conducted for the mITT population only.

12.1.9.1 Missing values in the components of the cognitive composite score

If at any given visit, where all four components are intended to be measured and one of the four components has missing scores, meaning less than 30% of the total components [6], then the composite will be calculated using only the other three components and with the method described in SAP [Section 4.2.1](#). But the composite will be weighed by 1/3 instead of 0.25. If two or more components have missing scores, then the composite will be considered missing as well.

If at any given visit, only some of the four components are intended to be measured instead of all, then the composite score will not be calculated and will not be used in the analysis for these visits.

12.1.9.2 The univariate 3-arm DPM (3-arm UDPM)

The **3-arm UDPM** (the active gantenerumab arm, the active solanezumab arm, and the mutation positive placebo arm) will be applied to the DIAN-TU-001 Cognitive Composite score as well as each of its components. The model behavior, the threshold to control type I error rate, and the estimated power are presented in [Appendix V](#).

12.1.9.3 Other analysis of the DIAN-TU-001 cognitive composite

The DIAN-TU-001 cognitive composite score will be analyzed using the LME model or the MMRM in the way they are specified in SAP [Sections 12.1.6.8](#), [12.1.6.9](#), and [12.1.7](#).

12.2 Analyses of Additional Efficacy Endpoints

The following analyses will be conducted for the combined population of the mITT population and the eligible DIAN-OBS subjects unless otherwise specified.

12.2.1 Analysis of a Cogstate Multivariate Endpoint

Because of the lack of Cogstate tests in DIAN-OBS, the following analyses will be conducted without using the eligible DIAN-OBS subjects.

A Cogstate Multivariate Endpoint will be analyzed similarly to the DIAN-MCE using the same MDPM. This Cogstate Multivariate Endpoint is composed of the following four tests: Cogstate Detection Task, Cogstate Identification Task, Cogstate One Card Learning Test, and Cogstate One Back Task. Measurements for each test will be normalized using its mean (SD) at DIAN-TU-001 baseline among mutation negative subjects before being analyzed. The MDPM and all its other parameters will be set up similarly as in [Section 12.1.3](#).

Each component of the Cogstate multivariate endpoint will be analyzed independently using the MMRM and LME model. The LME model and the MMRM will be set up in the same way as they are specified in SAP [Sections 12.1.6.8](#), [12.1.6.9](#), and [12.1.7](#) in terms of model setup and the corresponding analysis population.

12.2.2 Analysis of an Alternative Multivariate Endpoint

An alternative multivariate endpoint will be analyzed in the same way as the DIAN-MCE using the same MDPM. This alternative multivariate endpoint includes four tests: Logical Memory Test Immediate Recall, Trailmaking Test part B, Digit Span Backward Recall, and Category Fluency (Animals). Measurements for each test will be normalized using its mean (SD) at DIAN-TU-001 baseline among mutation negative subjects before being analyzed. The MDPM and all its other parameters will be set up similarly to [Section 12.1.3](#).

Each component of the alternative multivariate endpoint will be analyzed independently using the MMRM and LME model, respectively. The LME model and the MMRM will be set up in the same way as they are specified in SAP [Sections 12.1.6.8](#), [12.1.6.9](#), and [12.1.7](#) in terms of model setup and the corresponding analysis population.

12.2.3 Analysis of Clinical Efficacy Endpoints

Both the LME model and the MMRM will be used to analyze the clinical efficacy endpoints (in SAP [Section 4.2.2](#)) unless alternate analysis methods are specified. And these models will be set up in the same way as they are specified in SAP [Sections 12.1.6.8](#), [12.1.6.9](#), and [12.1.7](#) in terms of model setup and the corresponding analysis population. The following specifies the analysis models that will be used for each particular endpoint and that are different from the MMRM or LME model.

- i) The % of subjects whose CDR increased from baseline (binary outcome yes vs no) will be compared between each active drug arm and the mutation positive placebo arm using chi-squared tests. This comparison will be done by visit and overall, where overall is the last CDR which contributes to the analysis; it will also be done by baseline CDR (CDR 0 vs CDR >0) by overall.
- ii) Time from CDR 0 to CDR >0 (converters vs non-converters) for subjects with baseline CDR 0 and time to an increase in CDR for subjects with baseline CDR >0 (progressors vs non-progressors) will be analyzed using the Cox proportional hazards model with stratification by baseline CDR (CDR 0 vs CDR >0) for the mITT population. Converters are defined as those who started with CDR 0 and ended up with CDR >0 and maintained at CDR >0 in all subsequent

follow-up. Progressors are defined as those who started with CDR>0 and ended up with 0.5 and more increase and maintained at least 0.5 increase from baseline in all subsequent follow-up. The time-to-event analysis will be done for the converters and for the combination of converters and progressors.

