3.4 Method of Treatment Assignment and Randomization

A dynamic randomization procedure will first be used to randomize mutation positive subjects to either the gantenerumab arms or the solanezumab arms; next it will be used again to randomize the mutation positive subjects within each study drug arms (active treatment vs placebo) by a minimization strategy, to ensure balanced treatment assignment within each level of 9 stratification factors with relative weights. The mutation negative subjects are randomized similarly, but independently. The stratification factors, levels and weights are listed in Table 1.

Table 1: Stratification Factors, Level and Weight

Stratification Number	Stratification Name	Stratification Level	Stratification Weight
1	Baseline CDR-SB	1. 0 2. 0.5-1 3. 1.5-3 4. >3	15
2	Estimated years from symptom onset (EYO)	1. -15 to -11 2. -10 to -5 3. -4 to -1 4. 0 to +4 5. +5 to +10	10
3	Gene type	1. PSEN1 2. PSEN2 3. APP 4. Mutation negative	8
4	Years of education	1. <12 2. 12 3. 13-16 4. >16	5
5	Age at randomization	1. 18-40 2. 41-55 3. 56-80	5
6	Presence of APOE4 allele	1. Positive 2. Negative	3

Stratification Number	Stratification Name	Stratification Level	Stratification Weight
7	Region	1. United States / Australia / Canada 2. Europe 3. Rest of world	3
8	Study site	One level per site	3
9	Sex	1. Male 2. Female	1

The dynamic randomization algorithm is based on a technique described by Pocock and Simon [4] and Taves [5]. The algorithm is designed to balance treatment assignment along the marginal distribution of each factor for all currently enrolling study arms. A detailed description of the algorithm is given in the SAP [Appendix I](#). Randomization of each subject will occur at the baseline visit after all baseline assessments and prior to the first dose administration.

An Interactive Web Response System will be used for randomization, stratification, drug distribution management, drug re-supply, and subject discontinuation and will be implemented by an independent vendor.

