8.2 Type I Error Rate Control

The primary analysis for each study drug is based on a Bayesian posterior probability. This posterior probability of slowing the rate of cognitive decline is used to determine success on the primary efficacy analysis. The posterior probability threshold is selected to control the type I error rate for the multivariate analysis of DIAN-MCE. The type I error rate is the probability of rejecting the null hypothesis that there is no difference in cognitive decline or there is faster decline in the subjects in the active drug arm compared to those in the pooled control group with dynamic borrowing when the null hypothesis is true.

Although this study investigates multiple study drugs with shared placebos for the primary efficacy analysis, no adjustment for multiple drugs will be done. Each drug is considered to have its individual 2.5% type I error rate.

There will be no comparison between study drug arms.

For any secondary analyses based on the MDPM or UDPM, the test will be one-sided with a type I error rate of 0.025 for each analysis. For any secondary analyses based on the linear mixed effects (LME) model or the mixed-effects model for repeated measures (MMRM) or any other frequentist models, the test will be two-sided with a type I error rate of 0.05 for each analysis.

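### The CDR-increase comparison in SAP 12.2.3 item i ignores baseline CDR although allocation balances on it; the test is conservative (true size about 1.5-5%) and a CDR-stratified test would be better

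*SAP*

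**What the plan says.** SAP 12.2.3 item i takes as a binary outcome whether a subject's CDR rose from baseline. The proportions "will be compared between each active drug arm and the mutation positive placebo arm using chi-squared tests". This is done at each visit and overall, where overall means the last CDR that contributes to the analysis. The item adds that "it will also be done by baseline CDR (CDR 0 vs CDR >0) by overall". The split by baseline CDR is therefore planned for the overall comparison only, as two separate tests, with no combined stratified test.

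Item ii of the same section analyses time to CDR conversion or progression with a "Cox proportional hazards model with stratification by baseline CDR (CDR 0 vs CDR >0) for the mITT population".

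SAP 3.4 allocates subjects by minimization "to ensure balanced treatment assignment within each level of 9 stratification factors with relative weights". In Table 1 and Appendix I baseline CDR-SB has the largest weight (15), and a score of 0 forms its first level. EYO has the next largest weight (10).

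For secondary analyses by frequentist models, SAP 8.2 says that "the test will be two-sided with a type I error rate of 0.05 for each analysis".

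**The concern.** The Pearson chi-squared variance for a pooled two-by-two table assumes that the mix of baseline CDR 0 and CDR >0 subjects varies between arms as it would under simple randomization. Minimization on CDR-SB removes most of that variation. If CDR 0 and CDR >0 subjects worsen at different rates, the pooled variance is larger than the true variance of the arm difference. The test then rejects less often than 5% under the null and loses power under the alternative.

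The comparison is small, with about 52 active against 34 pooled placebo subjects, so there is little power to lose. Other analyses of CDR in the SAP do use the baseline state. Item ii stratifies by it, the linear mixed-effects (LME) model of 12.1.6.8 includes disease status defined by CDR >0, and the MMRM of 12.1.6.9 adjusts for the baseline score. The combined test in item i is the exception.

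**Working it through.** The SAP gives no event rate, power or true size for this test, so there is no figure of its own to reproduce except the nominal 5%. Under simple randomization (20,000 simulated trials, about 52 vs 35) the plain test gives 4.8-5.4%, so the nominal level is right when the allocation is not balanced.

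**Inputs from the SAP**
- Arm sizes: 52 active and 34 pooled placebo (drug appendices, section 3.4).
- Share with baseline CDR >0: at most 50% (3.2). At 50% this gives 26+26 active vs 17+17 placebo.
- Level: two-sided 5% (8.2).
- Minimization on nine weighted factors (3.4, Appendix I).

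**Assumptions**
- Increase rates p0 (baseline CDR 0) and p1 (baseline CDR >0).
- A common odds ratio (OR) of 0.4 for power.
- A biased-coin probability of 0.7-0.9, which the SAP does not state.
- Balance on CDR-SB levels stands in for balance on CDR 0 vs >0.

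**Is the balance real?** Simulating the nine-factor minimization with 140 subjects, the SD of the arm difference in the CDR >0 share falls from about 0.11 under simple randomization to 0.03-0.04. It is.

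**Size under exact balance.** Let q be the CDR >0 share and m = (1-q)·p0 + q·p1. Then

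V_marginal = m(1-m)

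V_within = (1-q)·p0(1-p0) + q·p1(1-p1)

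size = 2·[1 - Φ(1.96·√(V_marginal/V_within))]

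Two examples with q = 0.5:
- Rates 0.2/0.4: V_marginal = 0.3×0.7 = 0.21 and V_within = (0.16+0.24)/2 = 0.20. The ratio is 1.05 and the size 4.5%.
- Rates 0.2/0.8: V_marginal = 0.25 and V_within = 0.16. The ratio is 1.5625, so z = 1.96×1.25 = 2.45 and the size is 1.4%.

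**Simulation** of 200,000 tables per setting (26/17 in each stratum), plain Pearson vs CMH without continuity correction:

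| p0 / p1 | Gap (points) | Size, plain | Size, CMH | Power at OR 0.4, plain | Power at OR 0.4, CMH |
|---|---|---|---|---|---|
| 0.3 / 0.3 | 0 | 4.9% | 5.0% | 40.7% | 40.7% |
| 0.2 / 0.4 | 20 | 4.4% | 4.9% | 38.2% | 39.2% |
| 0.3 / 0.67 | 37 | 3.3% | 5.0% | 41.9% | 46.6% |
| 0.2 / 0.6 | 40 | 3.1% | 5.0% | 37.5% | 43.0% |
| 0.1 / 0.6 | 50 | 2.1% | 4.9% | 28.0% | 37.2% |
| 0.2 / 0.8 | 60 | 1.4% | 4.8% | 22.7% | 37.2% |

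**With minimization simulated instead of exact balance** (20,000 trials per setting), balance is slightly less tight and the plain test slightly less conservative. Its size is 4.4-4.9% at 20/40, 3.2-3.8% at 20/60, 2.6-2.9% at 20/70 and 1.7-2.0% at 20/80. CMH stays at 4.6-5.2% in every setting.

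**What gap gives 1.5-3%?** Solving the size formula over q = 0.3-0.5 and p0 = 0.1-0.3, the two rates must differ by about 39-64 points.

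**Does the SAP's own model imply such a gap?** Simulating CDR from the composite model of Appendix V gives a gap of only about 2-21 points over 2-6 years. By the formula, balance on CDR 0 vs >0 alone then leaves the size at about 4.5-5.0%. Adding balance on the EYO bands at years 4 and 6 brings it to 2.0-3.0% with the Appendix V random-intercept SD of 1, and to 1.5-2.3% with an SD of 0.5. In that model most of the loss comes from EYO.

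**The case against.** The strongest reply is that this is a minor efficiency matter on a supplementary test. The SAP gives no increase rates, its own simulation model suggests a modest gap, and at a 20-point gap the gain is about 1 point of power. Baseline CDR is handled nearby: item i repeats the overall comparison within CDR 0 and CDR >0, item ii is stratified, and global CDR is also analysed by LME and MMRM. No confirmatory decision rests on item i. The primary test is the multivariate disease progression model, and the gantenerumab testing sequence is CDR-SB then FAS, primarily by LME. The error is in the safe direction.

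Most of this stands, and it limits the weight of the point. It does not justify the pooled test. The split by baseline CDR covers only the overall comparison, uses about half the subjects in each test, and gives no combined result.

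Three stronger readings are tempting and not supported:
- A reader might infer that the test runs at 1.5-3% as a matter of fact. That needs a gap of roughly 40-60 points, which the SAP does not document.
- A reader might take rates such as 0.30 and 0.67 as implied by the SAP's composite and CDR model. The Appendix V model gave a gap of about 2-21 points.
- A reader might infer that items i and ii could disagree for no clinical reason. They measure different things. Item i counts any increase at a visit or at the last contributing CDR; item ii is a time-to-event analysis of an increase that must be maintained in all later follow-up. They can differ whatever the stratification.

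**Conclusion.** The point holds as an improvement to a supplementary analysis. The unstratified test in item i does not use a factor on which the allocation is most heavily balanced and by which item ii is stratified. If that factor predicts a CDR increase, the test is conservative, with a true size of about 1.5-5% depending on the gap between the CDR 0 and CDR >0 rates. If the rates are equal, nothing is lost. A CDR-stratified CMH test stays near 5% and showed no material loss of power in any setting examined.

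The result rests on assumed increase rates, a common odds ratio, a CDR >0 share near the 50% cap, and minimization that balances closely on CDR 0 vs >0. The simulated balance supports the last of these.

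**What to change.** In SAP 12.2.3 item i, replace the unstratified chi-squared test by a CMH test stratified by baseline CDR (0 vs >0), for each by-visit comparison and for the overall comparison. Report the common odds ratio with its 95% CI beside the crude percentages. Keep the tables by baseline CDR as they are. The solanezumab appendix already uses a CMH test for immunogenicity, so the method is not new to the plan.

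The cost is one sentence and one procedure option. The downsides are that the common odds ratio assumes a similar effect in both strata, and that stratifying by CDR alone does not recover any loss due to balance on EYO.

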3.3 Study Population for Solanezumab and Gantenerumab

The study population consists of individuals who either are known to have an Alzheimer's disease (AD) causing mutation or who don't know their gene status but are "at risk" for an autosomal dominantly inherited Alzheimer's disease (DIAD) mutation. To be eligible for the trial, subjects (mutation positive and negative subjects) must be either 1) cognitively normal between 15 years younger (-15) to 10 years older (+10) than their expected age at cognitive symptom onset or 2)

have mild symptoms of dementia (CDR 0.5 or 1) and are within +10 years of onset of the symptoms of dementia. Other inclusion criteria are specified in the protocol.

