20 APPENDIX VI. DETAILS OF CLINICAL TRIAL SIMULATIONS FOR DIAN-MCE

In order to characterize and understand the performance of the primary DIAN-MCE analysis, we carried out detailed simulations of the design under multiple scenarios as described in this section. The trial is simulated as described, including the accrual and randomization of subjects, pooling of placebos, inclusion of simulated DIAN-OBS data, drop-out rates of subjects and the timing of the analysis as detailed here. A variety of scenarios are simulated with the operating characteristics summarized. The base case scenario presents the best estimates for each of the parameters used to simulate the trial and subjects. The remaining 7 scenarios explore the sensitivity of the design to different possible truths. The assumptions made in this section are based on an analysis of the DIAN-OBS cohort (Data Freeze 11). This section provides an estimate of the power and type I error rate for each study drug.

In particular, we make the following assumptions for our base simulations:

- **Regimen Size:** 70 mutation positive subjects with 3:1 randomization (active to placebo) per arm (53:17 per arm, for 53:53:34 for each arm and the pooled placebo)
- **Distribution of EYO at enrollment:** Uniform between -15 and +10 EYO with a simulation of CDR-global as a function of EYO for trial inclusion ($CDR \leq 1$)

Modeling Cognitive Endpoint Progression: The assumed model for simulating subjects is assumed for simulating virtual subject data. Let \tilde{Y}_{ij} be the 4-dimensional vector of outcomes for subject i , at their j th visit. Let E_{ij} be the estimated years to symptom onset for subject i at visit j .

The distribution for each observation is assumed to be normally distributed:

$$\tilde{Y}_{ij} \sim N_4(\tilde{\mu}_{ij}, \Sigma).$$

The mean for variable v is modeled as

$$\mu_{ijv} = \gamma_{iv} + f(E_{i0} - \delta_i | \alpha_v) + \exp(\theta_{T_i}) [f(E_{ij} - \delta_i | \alpha_v) - f(E_{i0} - \delta_i | \alpha_v)]$$

where the random effect for variable v is simulated as

$$\gamma_{iv} \sim N(0, 1^2) \quad v=1, 2, 3, 4.$$

The random effect for EYO adjustment is simulated as

$$\delta_i \sim N(0, 2^2).$$

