4.1 Secondary Efficacy Endpoints

The rate of change over time will be assessed for the following secondary efficacy outcome measures: CDR-SB and FAS. In order to control the overall type I error rate for the study, the fixed sequence testing procedure [3] will be applied to adjust for multiple comparisons. If the primary endpoint analysis shows a statistically significant treatment effect, the secondary endpoints will be tested in the following order at a two-sided alpha of 0.05:

1. CDR-SB,
2. FAS.

These outcome measures will be primarily analyzed using the model specified in [Section 12.1.7](#) (LME dose escalation) in the mITT population. In addition, analysis using the DIAN-OBS data

will be applied. The LME model and MMRM as defined in the SAP [Sections 12.1.6.8](#) and [12.1.6.9](#) will also be applied.

1. The primary biomarker endpoint for gantenerumab is defined as the change from baseline to week 208 in the following biomarker outcome measure:

Amyloid PET binding: Composite [¹¹C] PiB partial volume corrected (regional spread function or RSF) standardized uptake value ratio (C-SUVr) (PiB_fSUVr_rsf_TOTCORTMEAN (the composite) [PiB-PET]).

It will be primarily analyzed using MMRM in the mITT population, as described in SAP Section 12.1.6.9, excluding the solanezumab arm, but including the gantenerumab arm and the mutation positive placebo arm.

Additional analytical models as described in Sections 12.1.6.8 (LME) and [12.1.7](#) (LME dose escalation) will also be applied. The LME model applied to the PiB-PET endpoint will be identical to the one used for the secondary efficacy endpoint except that data from solanezumab treated subjects will not be included.

2. Time to an increase in CDR-SB will be analyzed using the Cox proportional hazards model with stratification by baseline CDR (CDR 0 vs CDR>0) for the mITT population. Progressors are defined as an increase of 0.5 or more from baseline and maintaining at least 0.5 increase from baseline in all subsequent follow-up. The subgroups of patients with baseline CDR 0 (converters) and baseline CDR >0 (progressors) will also be analyzed separately.

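### The Cox models for CDR and CDR-SB progression leave out baseline EYO: the tests stay valid, but the hazard ratio is attenuated relative to the EYO-conditional one and some power is given away

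*SAP*

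**What the plan says.** SAP section 12.2.3 item ii states that time from CDR 0 to CDR above 0, and time to CDR increase in those already above 0, "will be analyzed using the Cox proportional hazards model with stratification by baseline CDR (CDR 0 vs CDR >0) for the mITT population". It adds: "The time-to-event analysis will be done for the converters and for the combination of converters and progressors". Appendix VII section 4.1 item 2 repeats the model for a second outcome: "Time to an increase in CDR-SB will be analyzed using the Cox proportional hazards model with stratification by baseline CDR". That item also analyses the baseline CDR 0 and CDR above 0 subgroups separately. No covariate is named in either place.

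Elsewhere the SAP treats EYO as a leading prognostic factor. Table 1 in section 3.4 gives it weight 10, second only to baseline CDR-SB (15). Appendix I lists it among the factors associated with response. It is the time scale of the primary model. Section 3.3 admits subjects who are "cognitively normal between 15 years younger (-15) to 10 years older (+10) than their expected age at cognitive symptom onset", so the CDR 0 stratum can span 25 years of disease stage.

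For frequentist secondary models, section 8.2 says "the test will be two-sided with a type I error rate of 0.05 for each analysis".

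**The concern.** Stratifying on CDR 0 versus above 0 removes only part of the prognostic spread. In Table 8 the mean composite falls by about 0.07 per year before onset, and by 0.2 to 0.5 per year between EYO +1 and +5. Two CDR 0 subjects at EYO -14 and EYO +1 are therefore unlikely to share a conversion hazard. In the converters-only analysis, and in the two separate CDR subgroups of Appendix VII, the single stratification factor is constant, so the model is unadjusted.

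A hazard ratio is non-collapsible. When a strong predictor is left out, high-risk subjects have their events first, and earlier in the less effective arm, so the risk sets drift apart in composition. The ratio moves toward 1 even if the arms were balanced at entry. Balancing on EYO does not prevent this. It also makes the unadjusted standard error too large for the actual variability of the estimate. At stake is the chance that a sparse analysis of delay to clinical conversion or progression detects a real effect, and how its ratio is read.

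**Working it through.** **Nothing to reproduce.** The SAP states no power, event count or hazard ratio for this analysis. The 95.9% in section 5 belongs to the MDPM.

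**Inputs from the SAP.** Two-sided 0.05 (section 8.2). From Appendix VI: 53 active against 34 pooled placebo ("53:17 per arm, for 53:53:34 for each arm and the pooled placebo"); EYO at entry "Uniform between -15 and +10 EYO with a simulation of CDR-global as a function of EYO for trial inclusion"; 7% annual drop-out; accrual over 975 days with 4 years for the last subject, so follow-up runs from 4 to 4 + 975/365 = 6.7 years. Disease curve and CDR model from Tables 8 and 9.

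**Assumed, because the SAP is silent.** Conditional hazard ratio 0.5 to 0.7; log-hazard gradient 0.05 to 0.25 per year of EYO; annual hazards at a reference EYO of 0.12 (CDR 0) and 0.35 (CDR above 0).

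**Step 1, parametric hazards.** The model is h(t) = h0,stratum(t) × exp(g × EYO + log HR × treatment), with allocation balanced on CDR and EYO bands. Each cell has 2,000 simulated trials, converters plus progressors combined, true conditional HR 0.50:

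| Gradient g | Events | HR as planned | HR with EYO | Power as planned | Power with EYO | Gain, points |
|---|---|---|---|---|---|---|
| 0.05 | 34.0 | 0.51 | 0.50 | 48.2% | 50.9% | 2.7 |
| 0.10 | 32.6 | 0.54 | 0.50 | 41.3% | 48.6% | 7.4 |
| 0.15 | 32.0 | 0.57 | 0.49 | 33.5% | 48.1% | 14.7 |
| 0.20 | 31.9 | 0.60 | 0.50 | 25.5% | 46.4% | 20.9 |
| 0.25 | 32.0 | 0.64 | 0.49 | 18.9% | 46.5% | 27.6 |

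- At HR 0.7 the gains are 2.1, 4.6, 9.1, 10.1 and 12.4 points. With no gradient the gain is about 0.
- Converters only at HR 0.5 (13 to 15 events): 2.3 points at g = 0.10 and 12.2 at g = 0.20.
- Annual visit times at HR 0.5: 5.1 points at g = 0.10 and 12.3 at g = 0.20.

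**Step 2, hand check of one row.** Schoenfeld: power = Φ(√(D·p·(1−p))·|log HR| − 1.96), with p = 53/87 and p(1−p) = 0.238. At g = 0.10, D = 32.6, so √(32.6 × 0.238) = 2.79. With HR 0.537, 2.79 × 0.622 − 1.96 = −0.23, giving 41%. This matches the simulated 41.3%.

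**Step 3, type I error.** Under the null, with g = 0.10 and 0.20, the planned test rejects in 4.2% and 4.5% of trials under simple allocation, and in 3.5% and 2.0% when allocation is balanced on EYO. With EYO in the model the figures are 4.8% to 5.1%. The planned test is conservative, not anti-conservative.

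**Step 4, the SAP's own disease model.** Here CDR paths come from the Table 8 composite curve and the Table 9 distributions, and treatment acts through the CPR. Some cells have only 300 to 500 trials, with a Monte Carlo error of 2 to 3 points.

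| Version of the CDR model | HR at 50% slowing, planned vs with EYO | Gain at 50% slowing | Gain at 30% slowing |
|---|---|---|---|
| Table 9, fixed CDR quantile per subject | 0.63 vs 0.60 | within 0.4–4.3 overall (30% to 70% slowing) | within the same range |
| Tables 8 and 9 as printed, residual SD 0.333 | 0.57–0.72 vs 0.53–0.70 | 3–9 | 1–6 |
| Fixed quantile, composite limited to −3.6 to 1.2 | 0.55 vs 0.45–0.46 | about 15 | about 8–9 |
| The same without that limit | not reported | 6–15 | 6–9 |
| Hard CDR cut-points, no visit noise, flattened Table 8 tail | 0.53–0.55 vs 0.41–0.43 | about 17–25 | about 7–13 |

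Further approximate runs gave 3 to 14 points with residual SD 0.333 and 10 to 34 with no noise. Converters-only gains were mostly 3 to 9 points, on about 9 to 14 events.

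Two things drive the spread. The first is how noisy CDR is around the composite. The second is the Table 9 tail: its untruncated normals make the probability of CDR 2+ fall from 0.92 at a composite of −4 to 0.43 at −5, which weakens the link between late EYO and progression.

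**The case against.** The strongest defence is that nothing here is wrong. The unadjusted ratio answers a marginal question, the adjusted one a conditional question, and the SAP does not claim the second. The test does not exceed its nominal level. Stratifying on CDR status mirrors the LME models of section 12.1.6.8, which also adjust only for CDR above 0. The analysis is not primary and is outside the gantenerumab fixed sequence (CDR-SB, then FAS). All of this stands, and it limits the point to efficiency. The LME parallel is imperfect, since a linear slope difference does not attenuate in the way a hazard ratio does.

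Three stronger readings are tempting but unsupported:

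- A reader might infer that the planned hazard ratio is biased or the test invalid. It is a different target, and the null rejection rate is at or below 5%.
- A reader might fix the loss at, say, 9 to 26 points. That size needs a gradient of roughly 0.12 to 0.25 per year with a strong effect, or hard CDR cut-points with no visit noise. The SAP gives no such gradient, and it draws CDR probabilistically with a residual SD of 0.333.
- A reader might take this as the only analysis of clinical progression. Section 12.2.3 item i compares the share of subjects whose CDR increased, and CDR-SB is also analysed by LME and MMRM.

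One further caution stands. Section 12.1.6.10 separates an enrollment EYO, based only on parental onset, from the analysis EYO. The SAP does not say which of them fed the minimization. The degree of conservatism depends on how closely the two agree; the attenuation does not.

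**Conclusion.** The point holds as an efficiency improvement to a supportive analysis. The direction is secure: if EYO predicts events within CDR strata, omitting it moves the hazard ratio toward 1 relative to the EYO-conditional value, makes the test conservative under EYO-balanced allocation, and loses power.

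The size is conditional on assumptions. It runs from near zero with a weak gradient, through about 3 to 15 points in most simulations based on Tables 8 and 9, to 25 points or more with a steep gradient and little CDR noise. These results assume a linear EYO effect and a block approximation to minimization. Even with EYO included, power stays low for moderate effects: about 17 to 24% at 30% slowing in the more favourable versions of the disease model. The change improves a weak analysis without making it a strong one.

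**What to change.** In section 12.2.3 item ii, keep the stratification by baseline CDR and add baseline EYO as a continuous covariate, using the analysis EYO of section 12.1.2. Do the same in Appendix VII section 4.1 item 2, including its separate CDR 0 and CDR above 0 analyses. Report the unadjusted hazard ratio as supportive and label which ratio is marginal and which conditional. If EYO is deliberately left out, state the reason.

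The cost is one term in each model and no new data. The reported ratio becomes conditional on EYO. With about 10 to 35 events, the type I error of the adjusted Wald test should be checked by simulation before the model is fixed: in one Table 9 variant (composite not truncated) it rejected in 6.5 to 8.5% of null trials, against 3 to 6% in the other versions of that set. The change should be made before unblinding, since under section 6.2 a later addition would have to be reported as post hoc.
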